**NCT03350724**

**Version Date: 10/06/2015**

*Protocol Title*

Patient Outcomes and Gingival Blood Flow using Laser Doppler Flowmetry  
Following the use of episil® on Free Gingival Graft Donor Sites

*Principal Investigator*

[name] M.B.A., D.M.D.

*Co-Investigators*

[name] D.D.S., M.S.

[name] B.D.S, M.S., M.S.D.

*Population*

The population will consist of 40 subjects, 18 years of age and over, females (non-pregnant or non-breast feeding) and males, with a general health status of ASA 1 or 2, and patients of record at UTHealth School of Dentistry in Houston, Texas requiring the gingival augmentation procedure, the free gingival graft. [Augmentation of gingival tissues may be considered an elective procedure. Elective surgical procedures are not routinely performed on pregnant and lactating women. Such procedures can be performed after childbirth and/or completion of lactation.] A total of 60 subjects will be consented to account for some subject's unwillingness or inability to continue in the study and non-compliance with study procedures and appointments.

*Number of Sites*

This will be a single site study at UTHealth School of Dentistry in Houston, Texas.

*Study Duration*

The duration of the study will be two years.

*Subject Duration*

The duration per subject will be three weeks.

*Background, Aim, & Hypothesis*

The free gingival graft (FGG) is a commonly used periodontal plastic surgery procedure for the augmentation of keratinized gingiva around teeth and implants. The FGG procedure uses a harvesting technique from the palate that leaves an open wound that heals by secondary intention, which can take 2 to 4 weeks. Mucogingival surgery has been shown to cause postoperative pain 3.5 times as much pain as osseous surgery and 6 times as much pain as soft tissue surgery. When bone is left exposed it tends to exaggerate the inadvertent postsurgical inflammatory response and increase postoperative pain. Wessel and Tatakis compared patient outcomes following subepithelial connective tissue graft (SCTG) and FGG procedures and indicated that FGG was associated with a greater incidence of donor site pain compared to SCTG donor site during the early postoperative period. There were significant differences between early (3-day) and late (3-week) pain levels for FGG donor sites. Pain in the palatal donor site at 3 days postoperatively was reported by

50% of SCTG subjects and 90% of FGG subjects; this difference was statistically significant. A previous study found similar results and attributed the poorer patient outcomes following FGG to differences in donor site harvesting techniques. In an 8-week observational study using a verbal descriptor scale to assess postoperative discomfort, Del Pizzo et al. reported postoperative discomfort at palatal donor sites during the first postoperative week in 100% of subjects treated with an FGG harvesting technique and in only 50% of subjects treated with a single-incision harvesting technique. Additionally, in a study on 228 subjects using questionnaires to assess postoperative pain, Griffin et al. reported FGG subjects were three times more likely than SCTG subjects to develop post-surgical pain during the first postoperative week.

Improving patient outcomes is important in clinical practice. Wessel and Tatakis found that even with the use of palatal stents to protect FGG donor sites, a greater incidence of donor site pain was found during the early healing period compared to SCTG. The results of their study suggested that there is opportunity to improve the postoperative protocols of commonly used soft tissue grafting procedures with more effective donor wound protection schemes.

At the present time, some type of wound covering over the palatal donor tissue site is considered a standard of post-operative care. While palatal stents are one option for protection of the palatal wound, other techniques have been utilized to aid in hemostasis and post-operative discomfort. Another technique utilizes a hemostatic agent such as Gelfoam® (absorbable gelatin compressed sponge) or Surgicel® covered with a wound dressing such as PeriAcryl®90 (a cyanoacrylate tissue adhesive).

A new wound dressing material, episil®, has shown to give rapid extended reduction of pain in cancer patients suffering from Oral Mucositis/Stomatitis (may be caused by chemotherapy or radiotherapy). The intended use of episil® is for the management of pain and relief of pain, by adhering to the mucosal surface of the mouth, soothing oral lesions of various etiologies. episil® has obtained 501(k) market clearance by the US FDA, in June 2011. episil® is an oromucosal liquid in a multi-dose container and is without active pharmaceutical ingredients and without systemic side effects demonstrated in clinical and pre-clinical studies. episil® is intended for use in the oral cavity as far as the pharynx but it is not dangerous to swallow. The oromucosal liquid transforms *in situ* to a bioadhesive oromucosal gel by uptake of small amounts of aqueous fluid. episil® contains six ingredients glycerol dioleate, soy phosphatidyl choline (lecithin), ethanol, propylene glycol, polysorbate 80 and peppermint oil which are all generally recognized as safe. No side effects have been reported. episil® contains small amounts of ethanol (alcohol), less than 100 mg per dose, which may cause a burning sensation when applied to sore mucosal surfaces. episil® contains also small amounts of propylene glycol which may cause skin irritation and peppermint oil which may cause allergic reaction. episil® should not be used on patients allergic to any of the ingredients, including peanuts, soy (soya) or peppermint oil. Currently there are no known concerns of use of episil® in human pregnancy or breast-feeding.

episil® is contained within an amber glass bottle with a manual metering pump filled with 10 mL of oral liquid. It is applied to the oral cavity by spraying 1 – 3 times. Distributed to affected areas in the mouth and within a few minutes the liquid converts to a gel and the protective film is formed. It is intended for use 2 – 3 times a day or as needed and is normally intended for continuous use for not more than 30 days.

Oral mucositis in advanced stages, similar to a FGG donor site, can be extremely painful, preventing a patient from eating and even disrupting the patient's daily functions. The aim of this study will be to compare patient-based outcomes, specifically postoperative pain, at the FGG donor sites, using an interventional parallel-group design, whereby a hemostatic gauze, Surgicel®, will be placed within all of the palatal donor sites and covered with either episil® (test) or a cyanoacrylate dressing, PeriAcryl®90 (control). The secondary aim of this study will be to compare gingival healing via measurement of the gingival blood flow at the FGG donor sites by the laser Doppler flowmetry (LDF) technique, by monitoring blood perfusion. The hypothesis for the present study is that patient-based outcomes and gingival blood flow will be more favorable for the FGG donor sites being covered by the test wound dressing material episil® compared to the control dressing.

#### *Study Population and Design*

Forty subjects will be recruited from the Periodontics and Dental Hygiene Clinic and the UTDentists Practice, located at the UTHealth School of Dentistry in Houston, Texas, where the study will be performed. Only subjects who have already formally agreed to receive a FGG as part of their overall periodontal treatment plan will be recruited. Inclusion criteria will be 18 years of age or older, patient of record at UTHealth School of Dentistry Houston Texas, signed treatment plan for a FGG, and the ability to provide research informed consent. Exclusion criteria will be any allergies to any of the ingredients in episil® including allergies to peanuts, soy or peppermint oil, smokers, pregnant or breast feeding women, and inability or unwillingness to provide informed consent. As stated above, elective surgical procedures are not routinely performed on pregnant or lactating women and are postponed until after childbirth and or completion of lactation. Exit criteria will be unwillingness or inability to continue in the study and non-compliance with study procedures and appointments. The Institutional Review Board of The University of Texas will approve the study protocol, questionnaires and informed consent form.

The study will be of an interventional parallel-group design. A computer generated randomization scheme will assign the subjects to one of the two treatment groups. All subjects will have the gingival grafting procedure, the free gingival graft, performed at sites lacking attached keratinized gingival tissues. The palatal donor site in subjects assigned to the control group will receive the hemostatic agent, Surgicel®, covered by the cyanoacrylate dressing, PeriAcryl®90. The palatal donor site in the subjects assigned to the test group will receive the hemostatic agent, Surgicel®, covered by episil®. Additionally, the subjects in the test group will be given the remainder of the bottle of episil® to take home with

instructions for self-application as needed 3 times daily for pain relief. A sufficient supply of the episil® will be provided to the test subjects for the study duration. The total duration of the study per subject will be 21 days from the day of the surgical procedure. The primary outcome of postoperative pain will be determined by the subjects recording their postoperative pain threshold using a Visual Analog Scale Form/Questionnaire and the number of analgesic pills taken each day at 1, 2, 3, 5, 7, 10, 14 and 21 days postoperatively. The Visual Analog Scale Form/Questionnaire for post-operative days 1, 2, 5 and 10 will be completed at the subject's place of residence, while the Visual Analog Scale Form/Questionnaire for days 3, 7, 14 and 21 will be completed at the subject's post-operative appointments at the dental clinic. The Visual Analog Scale Form/Questionnaire will evaluate the subjects' postoperative pain using a visual analog scale (VAS) scores from 1 to 10, with 1 indicating minimal pain and 10 indicating severe pain. If no pain is present, a score of 0 will be given. The levels of postoperative pain will be classified as none to minimum if the score is "0 to 3," moderate for "4 to 6," and severe for "7 to 10." None to minimal pain will mean little or no discomfort; moderate is any pain that bothers the subject and mildly affects normal function; and severe will be considered any pain that will not be tolerated and may even disrupt the subject's daily functions.

One of the secondary outcomes, gingival blood flow, will be determined with the laser Doppler flowmetry (LDF) technique to measure the blood perfusion of the FGG donor site and as well as the contralateral side of the palate, as a positive control, at baseline prior to surgery, immediately after harvesting of the FGG from donor site, and on post-operative days 3, 7, 14 and 21. The LDF technique is an unbiased non-invasive method of monitoring the response to periodontal therapy. It is adequate for recording changes in gingival blood flow following periodontal surgery presenting different patterns of microvascular blood flow alterations during the wound-healing period. The LDF technique is based on the Doppler principle. A laser beam will be emitted by an optical fibre onto the FGG donor site. The light hitting moving erythrocytes is scattered back in shifting frequency, which is the Doppler effect, and is captured by one or more optical fibers. The light signals are then converted into electric signals and the resulting photocurrent is processed to provide a recording of the blood flow. The term used to describe blood flow is flux – a quantity proportional to the average speed of the blood cells and their concentration. This is expressed in arbitrary perfusion units (PU), which are linearly related to flux. The PeriFlux System 5000 (Laser Doppler Blood Perfusion Monitoring and  $\text{tcpO}_2/\text{tcpCO}_2$ ) along with the Laser Doppler Probes for the PeriFlux System 5000 will be used to perform the LDF technique.

The other secondary outcome will be the time needed to obtain a complete re-epithelialization of the FGG donor site, and will be performed by a non-invasive peroxide test. This test is based on the principle that if the epithelium is discontinuous, the  $\text{H}_2\text{O}_2$  diffuses into the connective tissue; the enzyme catalase acts on  $\text{H}_2\text{O}_2$  to release water and oxygen: this is clinically shown by the production of bubbles on the wound. 3%  $\text{H}_2\text{O}_2$  will be applied to the FGG donor site with a syringe and the appearance of bubbles will be recorded as a dichotomous variable (yes/no) at the post-operative days 3, 7, 14, and 21 until a subject's FGG donor site has

completely epithelialized (no bubbles observed), when they will not be measured again at future post-operative visits.

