**First clinic visit (Screening visit):** Discussion of study and attain informed consult for participation in the study; medical history will be updated, vital signs will be taken, and an upper arch alginate impression will be taken in order to create a plastic stent, which will be worn during the laser Doppler flow measurements.

**Second clinic visit (Day of Surgery):** The day of surgery, the laser Doppler flowmetry readings will be performed before the surgery and then again immediately after harvesting of the FGG donor site. Subjects will receive 4 copies of the Visual Analog Scale Form/Questionnaire to be completed at their homes on days 1, 2, 5, and 10 postoperatively, which will be labeled accordingly. Subjects assigned to the test group will receive a manual-metering pump containing sufficient episil® for the duration of the study. Subjects in the test group will be instructed to use the pump up to 3 times a day. Instructions for home application of the episil® will be given orally and in writing at this appointment.

**Day 1 post-operative:** All subjects will complete at home the Day 1 Post-Operative Visual Analog Scale Form/Questionnaire.

**Day 2 post-operative:** All subjects will complete at home the Day 2 Post-Operative Visual Analog Scale Form/Questionnaire.

**Day 3 post-operative (3rd clinic visit):** All subjects will bring the 2 completed Visual Analog Scale Forms/Questionnaires to the day 3 post-operative clinic appointment and will complete the Day 3 Post-Operative Visual Analog Scale Form/Questionnaire during this appointment. The laser Doppler flowmetry readings will be performed on the free gingival graft donor site and on the contralateral side of the palate utilizing the fabricated stent with holes for the Doppler probe positioning for repeatability of readings. 3% H2O2 will be applied to the FGG donor site with a syringe and the appearance of bubbles will be recorded as a dichotomous variable.

**Day 5 post-operative:** All subjects will complete at home the Day 5 Post-Operative Visual Analog Scale Form/Questionnaire.

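### The allergy exclusion covers only episil, although Surgicel goes on every donor site and PeriAcryl 90 on every control site (minor)

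*Combined protocol and SAP*

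**What the plan says.** **Eligibility.** Study Population and Design gives one allergy criterion: "Exclusion criteria will be any allergies to any of the ingredients in episil® including allergies to peanuts, soy or peppermint oil, smokers". The list ends with "pregnant or breast feeding women, and inability or unwillingness to provide informed consent". Neither cyanoacrylate nor Surgicel appears in it.

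**Where the criterion comes from.** It matches the product warning in Background, Aim, & Hypothesis: "episil® should not be used on patients allergic to any of the ingredients, including peanuts, soy (soya) or peppermint oil". The documents give no corresponding warning for PeriAcryl 90 or Surgicel.

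**What is applied.** The aim paragraph says that "a hemostatic gauze, Surgicel®, will be placed within all of the palatal donor sites". For the control arm, Study Population and Design says: "The palatal donor site in subjects assigned to the control group will receive the hemostatic agent, Surgicel®, covered by the cyanoacrylate dressing, PeriAcryl®90".

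**Assignment.** "A computer generated randomization scheme will assign the subjects to one of the two treatment groups". No allergy condition is attached, and the plan does not say at which visit assignment takes place.

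**Screening.** At the first clinic visit, "medical history will be updated, vital signs will be taken". No criterion is tied to that history.

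**The concern.** Randomisation is fair to the subject, and to the comparison, only if everyone who is randomised could receive either assignment. Here the list screens for sensitivity to one of the three products placed on the wound. In ordinary practice a clinician can choose another covering for a patient with a known sensitivity, and the Background section itself describes alternatives such as palatal stents. Within the trial, random assignment removes that choice.

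Two things are at stake. The first is safety: read literally, the criteria admit a patient with a recorded sensitivity to a product that the plan then applies. The second concerns PeriAcryl 90 only. Patients with a known episil allergy are removed before assignment, and those with a known cyanoacrylate allergy are not. If such an allergy is found after assignment, the resulting switch or withdrawal can occur only in the control arm.

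**Working it through.** **1. Each product against the criteria**

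| Product | Who receives it | Allergy exclusion | Could a known allergy cause loss in one arm only? |
|---|---|---|---|
| episil | test arm | yes | no, screened out beforehand |
| PeriAcryl 90 | control arm | none | yes, control arm, if found after assignment |
| Surgicel | both arms | none | no, both arms are exposed alike |

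**2. Does another section close the gap?** The ASA 1 or 2 limit under Population grades general health and is not an allergy criterion. The medical history update at screening is a procedure with no eligibility rule attached. Data and Safety Monitoring deals with events once they have occurred. Its stop-use instruction is about episil, and its second paragraph covers unexpected, related and harmful events without naming a product. None of these is a screening rule, so the gap stands.

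**3. Exposure of an eligible allergic patient.** The Statistical Analysis section gives 20 subjects per group. Under equal allocation the chance of PeriAcryl 90 is 20/40 = 50%. The chance of Surgicel is 40/40 = 100%.

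**4. How often this might arise.** The documents give no allergy rate, so prevalence p is an assumption, varied from 0.1% to 5%. The chance of at least one affected subject among n is 1 − (1 − p)^n, and the expected number is n × p.

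| Assumed p | PeriAcryl 90, n = 20: chance | expected | Surgicel, n = 40: chance | expected |
|---|---|---|---|---|
| 0.1% | 2% | 0.02 | 4% | 0.04 |
| 0.5% | 10% | 0.1 | 18% | 0.2 |
| 1% | 18% | 0.2 | 33% | 0.4 |
| 2% | 33% | 0.4 | 55% | 0.8 |
| 5% | 64% | 1.0 | 87% | 2.0 |

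For example, at p = 1%: 1 − 0.99^20 = 0.182 and 1 − 0.99^40 = 0.331.

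**5. Effect on power.** The plan states no figure that bears directly on this point. As a yardstick, take a two-sided two-sample t-test at α = 0.05 and 80% power. The noncentrality is d × √(n₁n₂/(n₁ + n₂)), with f taken as d/2.

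| Controls | Test | Detectable d | f |
|---|---|---|---|
| 20 | 20 | 0.909 | 0.455 |
| 19 | 20 | 0.922 | 0.461 |
| 18 | 20 | 0.935 | 0.468 |

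Losing two controls raises the detectable f by 0.468 − 0.455 = 0.013. These values are not the plan's f = .57 for n = 40, which is stated for a repeated measures analysis whose inputs are not given. They serve only to show how little one or two losses matter.

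**The case against.** **The hazard is not documented.** The plan gives an ingredient warning for episil only, and it presents a hemostatic agent under PeriAcryl 90 as an existing technique. The one-product exclusion therefore follows the one warning that the documents contain. This is fair, and it is why no frequency can be claimed. It does not explain why eligibility should differ by product when assignment is random.

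**Routine care would catch it.** Subjects are patients of record, the history is updated at screening, and faculty supervise the surgery. A known allergy may well surface at the first visit, and nothing in the plan obliges anyone to apply a known allergen. Because the time of randomisation is not stated, discovery after assignment is a possibility and not a finding. This lowers the likely frequency, but the written list still makes the patient eligible.

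**Stronger readings that the documents do not support:**

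- *A Surgicel allergy would deplete the control arm.* It would not. Surgicel is used in both arms, so this is a safety gap for all subjects.
- *Losses overall would be one-sided.* This is not shown. Test subjects are told to stop episil after an adverse event, and the Background section mentions possible burning and irritation.
- *The results would be biased in favour of episil.* The direction is not established. A reaction in a retained control subject could worsen control outcomes, whereas withdrawing that subject would remove a poor result.
- *One or two subjects should be expected.* No rate supports this. Two expected among 20 controls would need a prevalence of 2/20 = 10%, and two among all 40 would need 2/40 = 5%.
- *Safety reporting covers episil alone.* Only the first paragraph of that section is so limited.

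**The real design gap is elsewhere.** The plan names no analysis population and no rule for subjects who cannot receive their assigned dressing. That is so, but it is a separate matter and no reason to leave the criterion incomplete.

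**Conclusion.** The gap is confirmed on the text: the exclusion addresses one of three products applied at the donor site, and no other section supplies the missing criterion. Its main consequence is an avoidable safety exposure. A secondary consequence, for PeriAcryl 90 only, is possible switching or loss in the control arm alone, conditional on the allergy being found after assignment.

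The size is uncertain and probably small. The probabilities above rest on an assumed prevalence and on 20 subjects per arm. The power cost is negligible, and no direction of bias can be claimed. Severity: minor, and worth correcting because the correction is so cheap.

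**What to change.** In Study Population and Design, extend the allergy exclusion to known hypersensitivity to any study product applied at the donor site: any episil ingredient (keeping the peanut, soy and peppermint oil examples), cyanoacrylate or PeriAcryl 90, and Surgicel. State that this is checked from the medical history at the screening visit, before randomisation.

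The cost is one sentence in the protocol and one line on the screening checklist. No new procedure or visit is needed. The downside is that an occasional patient may be excluded. The number cannot be estimated from the documents.

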#### *Data and Safety Monitoring*

Subjects will be informed that if they experience any adverse events with the use of episil®, that they should discontinue the use of the product immediately. Depending on the severity of the adverse event the patient will be advised to either call 911 or [name] to report the event. An Unanticipated Problems Tracking Log Form will be used to report adverse events to report them to CPHS. Any adverse event will then be immediately reported to Camurus AB, the manufacturer of episil®.

An Unanticipated Problems Tracking Log Form will be used to record and report any adverse events that are unexpected, related and put the subjects or others at harm, meet the definition of Unanticipated Problems Involving Risks to Subjects or Others and will be reported to the Committee for the Protection of Human Subjects.

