#### *Statistical Analysis*

Descriptive statistics will be expressed as means+/- SD and frequency distributions. Intergroup (FFG donor site using episil® and Surgicel® (test) and FGG donor site with PeriAcryl®90 and Surgicel® (control)) comparisons at 1, 2, 3, 5, 7, 10, 14 and 21 days will be analyzed by the Mann-Whitney U test. The Wilcoxon signed-rank test will be used for intragroup comparisons between 1, 2, 3, 5, 7, 10, 14 and 21 days. Differences in frequency distributions between the episil® group and the PeriAcryl®90 group will be analyzed by the Fisher exact test. Associations

between pain VAS scores and the number of analgesic pills or number of days analgesics were taken will be examined by the Pearson correlation coefficient. The significance level for rejection of the null hypothesis will be set at  $\alpha = 0.05$ .

All LDF recordings, which may be impaired by artifacts caused by the relative motion of the probe, will be excluded. An average of the 2-minute period of each individual recording will be calculated. Changes of blood flux values in the FGG donor site will be expressed as the difference ( $\Delta PU$ ) between the PU value at a specific site at a specific observation time point ( $PU_t$ ) and the individual baseline value of the same site ( $PU_0$ ):  $\Delta PU_t - PU_0$ .

Descriptive statistics will be performed using the SPSS statistical software. The  $\Delta PU$  values in the FGG donor site will be analyzed using the general linear model (GLM) univariate test, after verification of the assumptions of homogeneity of variance and normality of the residual distribution. The observation time and point and the position (mesial, center, distal and apical to the FGG donor site) will be modeled as fixed factors and the patient as a random factor with the  $\Delta PU$  as the dependent variable. The Dunnett two-sided *t*-test will be used, in order to evaluate the differences between baseline and subsequent time points and between different positions in the FGG donor site during the overall observational period. Data will be presented as mean SE. Statistical significance will be accepted at  $p < 0.05$ .

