The outcome analysis of the time needed to obtain complete re-epithelialization of the FGG donor site will be made by comparing experimental groups on the frequency distribution of patients experiencing complete re-epithelialization in each of the 4 post-operative visits. The Williams-adjusted log-likelihood ratio was performed, followed by *post-hoc* tests using Bonferroni-corrected Fisher's exact test (2-tailed).

Based on a sample size of  $n = 40$  (20 per group), a repeated measures analysis will have 80% power to detect an effect size of  $f = .57$ . For a sample size of  $n = 30$  (15 per group), the same analysis will have 80% power to detect an effect size of  $f = .67$ , while a sample size of  $n = 20$  (10 per group) will have 80% power to detect an effect size of  $f = .83$ . All of these effect sizes are classified as large effects by Cohen's guidelines (1988), or large differences in the change in pain score between the two groups.

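### Non-compliance is an exit criterion that can act after randomisation, and no analysis set limits its effect, so the daily pain comparison is open to bias of unknown direction

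*Combined protocol and SAP*

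**What the plan says.** **Exit rule.** Study Population and Design: "Exit criteria will be unwillingness or inability to continue in the study and non-compliance with study procedures and appointments". The section does not define non-compliance, say who judges it, or confine it to the time before randomisation.

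**Numbers.** The Population paragraph sets 40 subjects as the target and says "A total of 60 subjects will be consented to account for" unwillingness or inability to continue and non-compliance, taken together and counted from consent.

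**Assignment.** "A computer generated randomization scheme will assign the subjects to one of the two treatment groups". The moment is not given, but in the entry for the second clinic visit (day of surgery), "Subjects assigned to the test group will receive a manual-metering pump", so assignment has been made by then.

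**Follow-up.** "The total duration of the study per subject will be 21 days from the day of the surgical procedure". Pain forms are completed at home on days 1, 2, 5 and 10 and at clinic visits on days 3, 7, 14 and 21. Home forms are handed in at a later visit.

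**Home product.** Only the test arm has one. Data and Safety Monitoring tells subjects who have an adverse event with it "that they should discontinue the use of the product immediately".

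**Analysis.** Between-group comparisons on the eight pain "days will be analyzed by the Mann-Whitney U test". The Statistical Analysis section names no analysis set, no rule for data from exited subjects and no method for missing pain scores. Its only exclusion rule concerns blood-flow recordings with motion artefact. It adds that "a repeated measures analysis will have 80% power to detect an effect size of" f = .57 with 40 subjects, .67 with 30 and .83 with 20, without saying whether these are randomised, completing or analysed subjects.

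**The concern.** The primary outcome is pain reported by the subject. Randomisation makes the two groups comparable only while those analysed are those randomised. Most of what a subject can fail to comply with (eight forms and four post-operative visits) comes after assignment, so the exit rule acts mainly on randomised subjects. If removal is related to pain, and that relation or its frequency differs between arms, the Mann-Whitney comparison on each day can favour whichever arm loses more of its high-pain subjects. An exit around day 3 could also cost the day 1 and day 2 scores, because those forms are handed in at that visit. With no analysis set and no commitment to report exits by arm, a reader of the results could not tell whether this had happened.

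**Working it through.** **1. Order of events, from the protocol's own timeline.**

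| Step | When | Relative to assignment |
|---|---|---|
| Consent, impression for the stent | Screening visit | Not stated; before surgery |
| Dressing placed, home product given to test arm | Day of surgery | Assignment made by now |
| Home pain forms | Days 1, 2, 5, 10 | After |
| Visits with pain form, blood flow, peroxide test | Days 3, 7, 14, 21 | After |

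The exit rule can therefore remove subjects after randomisation.

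**2. The plan's own figures.** The allowance is (60 − 40)/60 = 33%, for all causes from consent. The split before and after randomisation is not given, so loss after randomisation could lie anywhere from 0 to 33%. The stated effect sizes can be approximated by a group-by-time F test with noncentrality f²N and degrees of freedom m − 1 and (N − 2)(m − 1). With m = 6 repeated measures (an assumption, since the plan gives no m), the detectable f at 80% power is 0.575, 0.667 and 0.826 for N = 40, 30 and 20. These figures concern power and say nothing about who is analysed.

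**3. Illustration of size.** None of these inputs is in the documents: normal pain scores, no true effect, the top fraction q of an exit propensity leaves an arm, the propensity correlates r with pain, exited subjects' data are dropped, and the subjects are replaced to 20 per arm.

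Mean shift of one arm in SD units = −r·φ(z)/(1 − q), with z = Φ⁻¹(1 − q).

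For q = 0.20: z = 0.842, φ(z) = 0.280, and 0.280/0.80 = 0.350. The shift is 0.2 × 0.350 = 0.070 SD at r = 0.2 and 0.5 × 0.350 = 0.175 SD at r = 0.5. The between-arm shift is the difference of the two arms' shifts.

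False-positive rates come from simulation (20,000 trials per cell, two-sided Mann-Whitney at 0.05).

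| Exits, arm A v arm B | r, A v B | Shift (SD) | False positives |
|---|---|---|---|
| 20% v 20% | 0.5 v 0.5 | 0 | about 5% |
| 20% v 10% | 0.5 v 0.5 | 0.08 | about 5.5% |
| 20% v 0 | 0.2 | 0.07 | about 5.5% |
| 20% v 0 | 0.5 | 0.175 | about 8% |
| 20% v 20% | 0.5 v 0 | 0.175 | about 8% |
| 20% v 20% | +0.5 v −0.5 | 0.35 | about 19% |
| One third in both | +0.5 v −0.5 | 0.55 | about 42% |

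Swapping the arms reverses the sign. Equal exit rates protect the comparison only if exit relates to pain in the same way in both arms. A stronger dependence on pain would give larger figures, so no row is a worst case.

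**4. Precision if exited subjects are not replaced.** The difference on a single day that a Mann-Whitney test detects with 80% power (normal scores, simulation) is about 0.94 SD with 20 per arm, 0.99 with 18, 1.06 with 16, 1.10 with 15 and 1.2 with 13. The last corresponds to one third of 20 leaving.

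**The case against.** The strongest case for the plan is that it never says exited subjects' data are discarded or that these subjects are replaced. A test done day by day can use whatever scores exist on that day, and scores recorded before an exit may well be kept. A subject who misses a visit gives no clinic score whether or not the criterion exists. Part of this stands: days before an exit are unaffected if their data are kept, and naming the analysis set is an essential part of the repair. But the criterion does more than record a missed visit. It ends participation, and so stops later pain scores that the subject might have given. The analysis section does not say that earlier scores are used.

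A reader might also infer that exits will be heavier in the test arm, because only that arm has a home product and an instruction to stop it after an adverse event. The documents do not support this. Home use is described as needed in one place and as up to three times daily in others, so light use is not clearly non-compliance. The adverse-event instruction stops the product, not participation.

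Nor does the allowance of 60 for 40 show a 33% loss after randomisation. It counts from consent, and losses before randomisation cause no bias between arms.

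**Conclusion.** The point holds as a risk, not as a demonstrated bias. The protocol states a rule that allows randomised subjects to be removed for non-compliance, and the analysis section contains nothing that limits the consequence. The direction is unknown. The size depends on how many exit, how exit relates to pain in each arm, and whether earlier data are kept, none of which is given. Under the assumptions shown, the effect is small when exits differ modestly in number and relate to pain alike (0.08 SD for 20% v 10% at r = 0.5). It is material when the relation to pain differs by arm (0.35 SD and about 19% false positives with equal 20% exits). It is absent if exits are unrelated to pain, or are equally frequent and related to pain in the same way in both arms. The sponsor should change the rule, because the protection is cheap and the harm could not be detected afterwards.

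**What to change.** 1. In Study Population and Design, delete non-compliance as an exit criterion. Keep withdrawal for subjects unwilling or unable to continue.
2. State that all outcomes are collected from every randomised subject willing to be followed, whether or not the home product is used or has been stopped.
3. In Statistical Analysis, state that every randomised subject is analysed in the assigned arm on all available days, including data recorded before any exit. Any analysis of compliers alone is a sensitivity analysis only.
4. Report exits by arm, timing and reason.

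Optional: one sensitivity analysis of the daily tests with missing pain scores ranked worst in both arms, since pain may still drive voluntary withdrawal.

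**Cost.** Protocol and analysis wording only, with no added patients or visits. Precision falls slightly on days with missing scores: the detectable difference rises from about 0.94 SD with 20 per arm to 1.10 with 15 and 1.2 with 13. Retaining subjects who depart from their assigned procedures may dilute the effect somewhat. For example, if 10 to 20% of test subjects gained nothing (assumed figures), the mean difference would shrink by the same 10 to 20%.
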